6.6.1 Collection of samples

Samples for determination of AZD6765 concentration in plasma will be analyzed by [REDACTED] on behalf of AstraZeneca. Full details of the validated bioanalytical method used will be provided in a separate bioanalytical report. Blood samples will be collected, labeled, and shipped as detailed below.

Additional analyses may be conducted on the biological samples to further investigate reproducibility of incurred samples. Any results from such analyses will only be used to

confirm the reproducibility of the method and will be reported in a separate table in the bioanalytical study contribution report.

Venous blood samples (6 mL) will be taken at the times presented below. Pharmacokinetic sample collection during or after dosing should not occur on the same arm used for drug administration, except samples taken prior to drug administration (ie, trough samples). Individual venipunctures for each time point may be performed or an indwelling catheter may be used. If a sample is taken through a catheter, the first 1 mL of blood will be discarded, and the catheter flushed after sampling with 2 mL of normal saline to keep it patent. Heparin may not be used to flush the catheter.

Six milliliter (6 mL) samples of whole blood will be collected into potassium ethylenediamine tetraacetic acid (K₂-EDTA) spray-dried tubes for the determination of AZD6765 in human plasma as follows:

Week 1: Infusion 1 at Visit 2 has 5 samples (0 hr, and 50 min, 2 hr, 3 hr, and 4 hr post dose)

Week 3: Infusion 9 at Visit 10 has 3 samples (0 hr, 70 min to 1.5 hr, 1.5 to 2 hr)

Week 6: Infusion 12 at Visit 13 has 3 samples (0.5 hr, 1.25 hr, 2 hr)

Week 12: Infusion 15 at Visit 16 has 3 samples (~1 hr, 70 mins to 1.5 hr, 2 to 4 hr)

All samples will be immediately placed on ice until centrifugation, which will begin within 30 minutes of sample collection. The sample will be centrifuged for 10 minutes at 2°C to 8°C at 1500Xg (a refrigerated centrifuge is not required, but the site must use a cooled centrifuge). The resulting plasma will be divided into 2 transfer tubes (USA Nunc 1.8-mL polypropylene round-bottom [free-standing] tubes with screw cap, or a tube approved by AstraZeneca) and immediately frozen upright at -20°C or below within 15 minutes of plasma preparation and kept frozen at this temperature before, during, and after transport to the designated laboratory. One of the samples will be retained at the site. AstraZeneca or representative will instruct the site when to ship the retention sample.

Samples will be drawn at random according to the PK sample schedule in [Table 9](#). All PK times given are based upon the time beginning at the start of the infusion, not relative to the end of the infusion. A maximum of 14 blood samples (approximately 84 mL) will be collected from each patient for PK assessments.

It is important that the actual date and time of the PK sample collection as well as the time and date and time of the administration of IP are recorded in the eCRF.

If a patient refuses blood collection for PK assessment, this will not be considered a protocol violation as the PK analysis is a secondary objective.

Table 9 Timing of PK sampling

	Visit	Infusion	1 st sample ^a	Subsequent samples ^a	Number of samples
Week 1	2	Infusion 1	0 hr (T ₀)	50 min, 2 hr, 3 hr and 4 hr	5
Week 3	10	Infusion 9	0 hr (T ₀)	70 min to 1.5 hr, 1.5 to 2 hr	3
Week 6	13	Infusion 12: ≥7 days from Infusion 11 in Week 5	0.5 hr	1.25 hr, 2 hr	3
Week 12	16	Infusion 15: ≥14 days from Infusion 14 in Week 10	~1 hr	70 min to 1.5 hr, 2 to 4 hr	3
Totals					14

^a T₀ samples should be drawn before infusion is started. Samples should be collected at random within the specified sample collection except where no window is given. It is paramount that samples must be drawn in the arm opposite to the infusion arm, except samples taken prior to drug administration (ie, trough samples). Samples scheduled to be drawn during the infusion period should be drawn while the infusion pump is still infusing. Actual sample collection date and time as well as dosing date and time must be recorded in the eCRF.

6.6.1.1 Labeling of AZD6765 plasma samples

Freezer compatible labels will be applied to the plasma sample tubes. The labels should contain the following information:

Study Number: D6702C00031

E-code:

Accession No.:

Visit No.:

Protocol Sampling Time:

Analyte: AZD6765

6.6.1.2 Shipment of AZD6765 plasma samples

All AZD6765 plasma samples accompanied by the sample shipment logs will be shipped via an agreed upon courier to the local [REDACTED] site. The frozen samples must be packed securely to avoid breakage during transit, should be double-bagged to contain leaks, and packed with a sufficient quantity of dry ice to ensure that the samples remain frozen for at least 72 hours to allow for delays in the shipment. All applicable shipping regulations must be followed. Documentation sufficient to identify each sample must be included with the shipment.

The primary monitoring scientist at AstraZeneca or representative must be notified by email and fax at the time that the samples are shipped. The fax notification should include a copy of the sample shipment log and courier tracking numbers.

Samples should only be shipped on Monday through Tuesday. Do not ship on or within 2 days prior to a legal holiday.

6.7 Pharmacodynamics

6.7.1 Collection and processing of serum samples for the determination of biomarkers

Venous blood samples (2 mL) (Table 10) for determination of biomarkers will be collected at the times presented in Table 4. Blood will be collected, labeled, and shipped as detailed below. The date and time will be recorded on the appropriate eCRF.

Serum sample

Blood will be collected according to site procedure. Individual venipunctures for each time point may be performed or an indwelling catheter may be used. If a sample is taken through a catheter, the first 1 mL of blood will be discarded, and the catheter flushed **after** sampling with 2 mL of normal saline to keep it patent. Heparin may **not** be used to flush the catheter.

The blood samples (2 mL) will be collected into red top tubes and processed according to standard laboratory procedures. The samples will be centrifuged for 10 minutes at 2°C to 8°C at a relative centrifugal force of 1500Xg (a refrigerated centrifuge is not required, but the site must use a cooled centrifuge). The resulting serum will be transferred to two 1.8 mL (Nunc Cryovial, Fisher Scientific No. 12-565-163N, NNI No. 375418) or a tube approved by AstraZeneca) and immediately frozen upright at -20°C or below within 15 minutes of serum preparation and kept frozen at this temperature before, during, and after transport to the designated laboratory. One of these samples will be retained at the site until instructed by AstraZeneca or representative. This retention sample will be retained until analysis is completed on the original sample and it is decided that the retention sample can be destroyed.

Please see Section 7.5 for withdrawal of informed consent for donated biological samples.

6.7.2 Labeling of serum samples for determination of biomarkers

Freezer compatible labels will be applied to the cryovials. The labels should contain the following information:

Study Number: D6702C00031
Patient Number:
Site Number:
Sample Number: (Tube and Set Number)

Week:
Visit:
Protocol Sampling Time:

██████████
Dose Number:
Analyte: AZD6765
Matrix: Serum

6.7.3 Shipment of serum samples to Rules Based Medicine Laboratories

All serum samples accompanied by the specimen shipment logs will be shipped via an agreed upon overnight courier to the local ██████████ site. The frozen samples must be packed securely to avoid breakage during transit, should be double-bagged to contain leaks, and packed with a sufficient quantity of dry ice to ensure they remain frozen for at least 96 hours to allow for delays in shipment. All applicable shipping regulations must be followed. Documentation sufficient to identify each sample must be included in the shipment.

The primary monitoring scientist at AstraZeneca or representative must be notified by email and fax at the time samples are shipped. The fax notification should include a copy of the specimen shipment log.

Samples should only be shipped on Monday through Wednesday. Do not ship on or within 2 days prior to a legal holiday.

6.8 Pharmacogenetics

6.8.1 Collection of samples

The blood sample for genetic research will be obtained from the patients at Visit 2 prior to randomization. Although genotype is a stable parameter, early sample collection is preferred to avoid introducing bias through excluding patients who may withdraw due to an AE, such patients would be important to include in any genetic analysis. If for any reason the sample is not drawn at Visit 2, it may be taken at any visit until the last study visit. Only 1 sample should be collected per patient for genetics during the study. Samples will be collected, labeled, stored, and shipped as detailed in the Laboratory Manual.

AstraZeneca intends to perform genetic research on AZD6765 to explore how genetic variations may affect the clinical parameters associated with AZD6765. Collection of DNA samples from populations with well described clinical characteristics may aid in the identification of future drug targets and projects to validate identified targets.

Refer to [Appendix D](#) for collection of PGx samples for the optional genetic research.

For blood volume, see Section [7.1](#).

6.9 Health economics (Not applicable)

7. BIOLOGICAL SAMPLING PROCEDURES

7.1 Volume of blood

The total volume of blood that will be drawn from each patient in this study is as follows:

Table 10 Volume of blood to be drawn from each patient

Assessment		Sample volume (mL)	No. of samples	Total volume (mL)
Safety	Clinical chemistry (including glucose, serum pregnancy, and lithium)	3	5	15
	Hematology (without HgbA _{1c})	2	2	4
	Hematology (including HgbA _{1c})	3	2	6
Thyroid function tests		2	1	2
FSH		1	1	1
HIV, HBsAg, HCV		6	1	6
Pharmacokinetics (AZD6765 levels)		6	14	84
Pharmacodynamics (optional biomarker analysis)		2	2	4
Pharmacogenetics (optional)		9	1	9
Total^a			32	131

^a The total volume given is the upper limit of volume of blood to be drawn for scheduled assessments. The FSH sample will only be collected from women <50 years old who could be considered postmenopausal and the pharmacogenetic and biomarker samples are optional.

For patients who participate in optional genetic sampling, a 9 mL blood sample will be collected after randomization.

For patients who participate in optional serum biomarker analysis, a 2 mL blood sample will be collected at randomization and at Week 6.

7.2 Handling, storage and destruction of biological samples

The samples will be used up or disposed after analyses or retained for further use as described here.

The laboratory will provide detailed instructions including processing, handling, storage, and shipment of laboratory samples before the study start. The samples should be properly obtained, processed, labeled, stored, and shipped in accordance with the instructions provided by the laboratory. Samples should be shipped to the laboratory by courier unless otherwise agreed.

7.2.1 Pharmacogenetic samples

The processes adopted for the coding and storage of samples for genetic analysis are important to maintain patient confidentiality. Samples will be stored for a maximum of 25 years, from the date of the Last Patient's Last Visit, after which they will be destroyed. DNA is a finite resource that may be used up during analyses. Samples will be stored and used until no further analyses are possible or the maximum storage time has been reached.

For all samples irrespective of the type of coding used, the DNA will be extracted from the blood sample. The DNA sample will be assigned a unique number replacing the information on the sample tube. Thereafter, the DNA sample will be identifiable by the unique DNA number only. The DNA number is used to identify the sample and corresponding data at the AstraZeneca genetics laboratories, or at the designated contract laboratory. No personal details identifying the individual will be available to any person (AstraZeneca employee or contract laboratory staff working with the DNA).

The samples and data for genetic analysis in this study will be single coded. The link between the patient enrollment/randomization code and the DNA number will be maintained and stored in a secure environment, with restricted access WITHIN the Clinical Genotyping Group Laboratory Information Management System (LIMS) at AstraZeneca. The link will be used to identify the relevant DNA samples for analysis, facilitate correlation of genotypic results with clinical data, allow regulatory audit, and to trace samples for destruction in the case of withdrawal of consent when the patient has requested disposal/destruction of collected samples not yet analyzed.

Refer to [Appendix D](#) for collection and storage of PGx samples.

7.3 Labeling and shipment of biohazard samples

The PI ensures that samples are labeled and shipped in accordance with the Laboratory Manual and the Biological Substance, Category B (materials containing or suspected to contain infectious substances that do not meet Category A criteria (see [Appendix C](#) "International Airline Transportation Association (IATA) 6.2 Guidance Document").

Any samples identified as Infectious Category A materials are not shipped and further samples taken from the patient unless agreed with AstraZeneca or representative and appropriate labeling, shipment, and containment provisions are approved.

It is the responsibility of the PI to ensure that staff packing the samples for shipment are IATA certified.

7.4 Chain of custody of biological samples

A full chain of custody is maintained for all samples throughout their life cycle.

The PI at each site keeps full traceability of collected biological samples from the patients while in storage at the site until shipment or disposal (where appropriate) and keeps documentation of receipt of arrival.

The sample receiver keeps full traceability of the samples while in storage and during use until used or disposed of or until further shipment and keeps documentation of receipt of arrival.

AstraZeneca or representative will keep oversight of the entire life cycle through internal procedures, monitoring of study sites, and auditing of external laboratory providers.

The CRO is responsible for keeping oversight of the samples during the study.

Samples retained for further use are registered in AstraZeneca's bio bank system during the entire life cycle.

7.5 Withdrawal of informed consent for donated biological samples

If a patient withdraws consent to the use of biological samples donated, the samples will be disposed/destroyed, if not already analyzed and the action documented. If samples are already analyzed, AstraZeneca or representative is not obliged to destroy the results of this research.

As collection of the biological samples is an integral part of the study, then the patient is withdrawn from further study participation.

The PI:

- Ensures patients' withdrawal of informed consent to the use of donated samples is conveyed immediately to AstraZeneca or its representative.
- Ensures that biological samples from that patient, if stored at the study site, are immediately identified, disposed of/destroyed, and the action documented.
- Ensures the laboratory(ies) holding the samples is/are informed about the withdrawn consent immediately and that samples are disposed/destroyed, and the action documented and the signed document returned to the study site.
- Ensures the patient and AstraZeneca or its representative are informed about the sample disposal.

AstraZeneca or representative will ensure the central laboratory holding the samples is informed about the withdrawn consent immediately and that samples are disposed/destroyed and the action documented returned to the study site.

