Patients should be semi-recumbent in a bed or reclining chair such that their feet are at the same level as their torso during the iv infusion. Patients will receive multiple infusions of AZD6765 (50 mg or 100 mg) or placebo during the treatment period. For visits with a scheduled infusion and MADRS assessment, the MADRS assessment should be given prior to the infusion.

Blood samples will be collected for PK analysis at specified visits during Weeks 1, 3, 6, and 12 (see [Table 9](#) for blood sampling schedule for all patients during the study).

This study includes the option for randomized patients to participate in optional exploratory genetic research and optional biomarker analysis, where permitted. A 9 mL sample of blood will be collected from qualified patients who have also provided consent for optional exploratory genetic research. The blood sample for genetic research will be collected anytime after a patient has qualified for the study, but it is preferred that collection be done at the baseline/randomization visit (Visit 2, Day 1). The serum sample for biomarker analysis will be collected at baseline/randomization visit (Visit 2, Day 1) and at Visit 13.

Weeks 2 and 3: Visits 5 to 10 (Days 8 to 21, Infusions 4 to 9)

During Weeks 2 through 3, all patients will receive 3 infusions per each week on non-consecutive days ([Table 4](#)). Each infusion will be given over 60 minutes.

At designated visits when the QIDS-SR-16 is administered, it must always be done prior to any other procedure in a quiet room without staff input as specified. After medical clearance and confirming negative urine pregnancy test, urine drug screen, and confirmation that the

patient is taking no prohibited concomitant medications, MADRS, CGI-S, CGI-I, HAM-A, S-STS and CogState will be administered prior to infusion during the visits specified on [Table 4](#). The CADSS and C-SSRS will be administered after the infusion. The S-STS self report version must be reviewed by the investigator during the C-SSRS interview and signed by the investigator.

During Weeks 2 and 3, patients will remain on site for at least 1 hour from the end of infusion (ie, up to T₂).

Patients must report by telephone any AEs that occur after the first infusion (Infusion 1 after randomization [Week 1]).

Weeks 4, 5, and 6: Visits 11 to 13 (Days 22 to 42, Infusions 10 to 12)

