7.5.1 Procedures for discontinuation from optional genetic aspects of the study

Patients who discontinue from the study should always be asked specifically whether they are withdrawing or continuing their consent for this linked genetic research. It must be established whether the patient:

- Agrees to the optional genetic sample and any DNA extracted from the sample being kept for genetic analyses in the future.
- Withdraws consent for the sample to be kept for the optional genetic analysis in the future and wishes the sample to be destroyed. Destruction of the sample (or the DNA extracted from the sample) will only be possible so long as the particular sample is traceable. In the event that genetic research has already been performed, AstraZeneca or representative will retain the results and associated data for regulatory reasons, but these will not be used in any subsequent analyses.

The PI is responsible for providing written notification to AstraZeneca or representative of any patient who has withdrawn consent for the use of the sample taken for genetic research. AstraZeneca or representative will provide written confirmation to the investigator of the actions taken with the sample, which must be filed in the investigator study file.

In the case of any patient withdrawing consent for the genetic research, the PI must notify the monitor using the “Withdrawal of Consent Form” (to be supplied). Requests for sample destruction should be forwarded by the monitor to the head of Clinical Genotyping Group along with copies of the relevant documentation detailing study code and patient enrollment code. AstraZeneca or representative and the PI will receive written confirmation from the Clinical Genotyping Group that the genetic sample has been destroyed.

If the withdrawal of consent for donated biological samples is limited only to the pharmacogenetic samples, the patient need not necessarily be withdrawn from further study participation.

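### Section 7.5 withdraws patients from the study for revoking consent to donated samples, which conflicts with the optional status of the biomarker and genetic samples

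*Protocol*

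**What the plan says.** Section 7.5 has a broad trigger: "If a patient withdraws consent to the use of biological samples donated, the samples will be disposed/destroyed". No sample type is named or excluded. The consequence is mandatory and comes with its reason: "As collection of the biological samples is an integral part of the study, then the patient is withdrawn from further study participation".

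The biomarker section refers to this rule: "Please see Section 7.5 for withdrawal of informed consent for donated biological samples" (Section 6.7.1). Section 3.1.2 offers randomized patients "optional exploratory genetic research and optional biomarker analysis, where permitted", and says that the Week 6 serum sample is taken only from patients who consented to that research. The footnote to Table 10 in Section 7.1 states that "the pharmacogenetic and biomarker samples are optional". Table 4 and the synopsis also label the biomarker sampling optional.

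The single exemption is in Section 7.5.1, for a withdrawal "limited only to the pharmacogenetic samples, the patient need not necessarily be withdrawn from further study participation". Section 5.9 and Appendix D, Section 3.1.4, are firmer: a patient may leave the genetic research at any time, independently of any decision about the rest of the study. Appendix D then refers to Section 7.5 for the procedure.

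On pharmacokinetics, Section 6.6.1 says: "If a patient refuses blood collection for PK assessment, this will not be considered a protocol violation". The reason given is that PK is a secondary objective.

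**The concern.** The rule in 7.5 rests on the premise that sampling is essential to the study. For the biomarker samples the protocol says the opposite, yet its own cross-reference brings them under the rule. The outcome is odd. A patient who never gives an optional biomarker sample stays in the trial, while one who gives it and later wants it destroyed is removed.

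Three things are at stake. First, a patient willing to continue loses further participation for an administrative reason, and Section 5.9 describes study withdrawal as covering both investigational product and assessments. Second, continued participation comes to depend on leaving an optional research consent in place. Third, post-randomization withdrawals are created that serve no scientific purpose, in a trial that does not replace patients (Sections 5.2.1 and 5.9) and that sets out in Section 12.2.6 to keep missing data low. Sites also face conflicting instructions for the genetic samples.

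**Working it through.** **Comparison of the texts, by sample type**

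| Sample | Status in the protocol | Effect of withdrawing consent to use | Consistent? |
|---|---|---|---|
| Biomarker serum | Optional (synopsis, 3.1.2, Table 4, 7.1) | 6.7.1 points to 7.5: withdrawn from study | No |
| Pharmacogenetic | Optional; leaving is independent of the main study (5.9, Appendix D 3.1.4) | 7.5.1: withdrawal not necessarily required, so still possible | No |
| PK plasma | Secondary objective; refusing collection is not a violation (6.6.1) | 7.5 has no exemption: withdrawn from study | Doubtful; refusal and revocation are different acts |

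Section 5.9 also lists patient-specific reasons for discontinuing a patient. Revoking sample consent is not named among them.

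**What happens to the endpoint data**

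1. Section 5.9 asks a patient who discontinues after at least one dose to return for the remaining scheduled visits, with MADRS among the assessments.
2. Section 12.2.6 includes these retrieved data in the main efficacy analysis.
3. Section 7.5 neither applies nor cancels these visits. Loss of further study treatment follows from its text; loss of MADRS does not.
4. A patient withdrawn after Visit 13 already has the Week 6 MADRS.

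**Size, starting from the plan's own figures**

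Inputs from Section 12.3: difference 5.5, SD 10, one-sided alpha 0.0125, power 90%, 10% information loss.

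- n per arm = 2(z₀.₉₈₇₅ + z₀.₉₀)²·SD²/difference² = 2(2.241 + 1.282)²·100/30.25 ≈ 82.1, so 83 by the normal approximation. A noncentral-t check at n = 84 gives power 0.9025, which reproduces the stated 84.
- 84/0.90 = 93.3, so 94 per arm; 3 × 94 = 282. Reproduced.

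The documents give no rate of sample-consent withdrawal. As an assumption, let an extra proportion x of each arm leave under 7.5 before Week 6 with no MADRS retrieved. Then n = 94 × (1 − 0.10 − x), and power = Φ(difference/(SD·√(2/n)) − z). The second power column uses the difference of 4.5 and two-sided alpha of 0.05 from Administrative Change 1.

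| x (assumed) | n per arm | Power, 5.5, one-sided 0.0125 | Power, 4.5, two-sided 0.05 |
|---|---|---|---|
| 0% | 84.6 | 0.909 | 0.833 |
| 2% | 82.7 | 0.902 | 0.825 |
| 5% | 79.9 | 0.892 | 0.812 |
| 10% | 75.2 | 0.871 | 0.788 |

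The loss is 0.7 to 0.8 points at 2%, 1.7 to 2.1 at 5% and 3.8 to 4.5 at 10%. If all MADRS scores are retrieved, n is unchanged. Those scores would come from patients no longer receiving infusions, so they could slightly dilute the contrast. The documents give no basis for putting a number on that.

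**The case against.** The best defence is that the protocol already limits the damage. Section 5.9 asks dosed patients back and Section 12.2.6 uses their scores. A reader might infer from 7.5 that primary-endpoint data are lost outright; the documents do not support that. Section 5.9 does describe withdrawal as covering assessments, but the same section goes on to ask discontinued patients to return. This part of the defence stands, and the claim about data is limited to risk.

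A reader might also infer that Section 6.6.1 contradicts 7.5 directly for PK samples. It does not. Section 6.6.1 concerns refusing a blood draw; 7.5 concerns revoking consent to use samples already given. Section 6.6.1 does not say in so many words that a patient who refuses stays in the study, and PK is a stated secondary objective. What remains is that calling sampling essential sits poorly with treating refusal as no violation.

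Finally, the frequency is unknown and probably low, so the statistical cost is small. It would also be wrong to measure such losses against the 30 patients between 282 and 252. That gap is an information allowance after recovery by the repeated-measures model, not a count of dropouts; the expected 14% dropout by Week 6 is about 39 of 282 patients.

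None of this removes the conflict over the optional biomarker and genetic samples, and retrieving scores does not restore participation to a patient who wanted to continue.

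**Conclusion.** The point holds as an internal contradiction with an avoidable consequence. It is clear for the biomarker samples, where an optional sample falls under a mandatory withdrawal rule. It is also clear for the pharmacogenetic samples, where the permissive wording of 7.5.1 leaves open what Section 5.9 and Appendix D rule out. For PK samples the text is unclear rather than contradictory.

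The case rests on consistency of consent and needless withdrawal, not on power. The power cost through lost sample size is probably under 1 point. That figure assumes no more than about 2% extra loss; the rate is an illustration with no source in the documents. The sample size of 282 reproduces and is not in question.

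**What to change.** Reconcile Sections 7.5 and 7.5.1 with Sections 3.1.2, 5.9 and 7.1 and Appendix D, Section 3.1.4:

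- State that withdrawing consent for optional biomarker or pharmacogenetic samples leads only to destruction of samples not yet analysed and no further sampling of that type, and does not by itself trigger withdrawal from the study.
- Bring the permissive exemption in 7.5.1 into line with this.
- State how 7.5 applies to PK samples, in light of Section 6.6.1.
- State that the follow-up assessments in Section 5.9, including MADRS, apply to any patient who is withdrawn under 7.5.

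The cost is protocol wording, with matching consent-form wording where it repeats the rule. Sample size, procedures and analysis do not change.
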